## **Research Design and Methods**

The overall goal of this proposal is outlined in the specific aims section. Specifically, we will target anorectal diagnostics of LARS patients to be conducted in the Department of Surgery at Prince of Wales Hospital in Hong Kong. In both studies listed below, we aim to recruit a heterogeneous group of patients to allow us to assess the effect of several underlying risk factors. In both studies, we will study the patients after closure of defunctioning stoma as we deem it impossible to carry out anorectal functional studies in patients with low rectal cancer before their rectal cancer surgery and assessing anorectal function post LAR before defunctioning stoma closure will produce unreliable, irrelevant data.

### Study Protocol:

Following ethics approval, patients will be assessed for their eligibility to participate in the trial. The PI and collaborators who are Good Clinical Practice (GCP) trained will recruit patients who are eligible for the study. Information sheet will be given to the patient in the surgical clinic, and written consent will be obtained at the next hospital visit. Ethics approval for this study will be granted prior to the start of the trial. The trial will be compliance with the Declaration of Helsinki. The trial will be registered in [www.clinicaltrials.gov](http://www.clinicaltrials.gov).

### Data collection:

Patients will be assessed at baseline and following will be recorded for all patients:

- Demographic data
- Body Mass Index (BMI)
- Significant Past Medical and Surgical History
- Obstetric History (female patients only)
- Rectal Cancer stage: TNM staging, location of tumour from anal verge on preop image

- Rectal Cancer treatment
  - o Neoadjuvant chemoradiotherapy/radiotherapy/chemotherapy
  - o Surgery – Open/Laparoscopic/Robotic/TaTME, level of anastomosis
  - o Post-operative complications
  - o Postop chemotherapy / radiotherapy
  - o Timing of defunctioning stoma (ileostomy / colostomy) closure
- LARS questionnaires: to assess Quality of life associated with LARS (Figure 4)

All patients will undergo the following tests:

- Integrated Fecobionics anorectal test (see clinical workflow below)
- High Resolution Anorectal Manometry (ARM) to assess resting and squeeze pressures, sensitivity, rectal capacity and recto-anal inhibitory reflex.
- Conventional balloon expulsion test
- Defaecography

Clinical data will be recorded and stored electronically in the hospital server. Completed questionnaires will be recorded and entered into database software and stored in the hospital server.

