## **Background of research**

Colorectal Cancer is the commonest cancer diagnosed for both genders combined in Hong Kong. In 2015 16.6% of all new cancer cases registered on the Hong Kong registry were cancer of colon and rectum. Distal colon cancer is more common than proximal colon cancer, with up to 38% of cancers being found in the rectum. Curative surgical treatment option for rectal cancer involves excision of tumour with 5cm proximal and 2cm distal margin with its draining lymphatics. The level of anastomosis or need for temporary or permanent stoma will depend on the height of tumour from the anal verge, extent of local invasion, the sphincter function preoperatively, co-morbidity and whether they required preoperative chemoradiotherapy. With neoadjuvant chemoradiotherapy offering potential tumour shrinkage and improvements in surgical technique such as the transanal total mesorectal excision (TaTME) technique offering accurate distal resection margin, many patients are now receiving sphincter-preserving surgery with low colorectal or coloanal anastomosis to avoid permanent colostomy. Up to 80% of patients who has undergone low anterior resection (LAR) suffer from severe bowel dysfunction post operatively. Patients symptoms typically fall into two categories: those with incontinence, frequency, and urgency, and those with constipation and feelings of incomplete emptying. However, some patients report features of both, either occurring simultaneously or fluctuating between these two groups of symptoms. This combination of symptoms after LAR is referred to as Low Anterior Resection Syndrome (LARS) which is associated with negative impact on quality of life (QoL). Originally, it was thought that these symptoms were short-lived neorectal irritability in the postoperative period. However, many studies report that the majority (up to 90%) of patients experience long-term changes in quality of life after LAR^6. Therefore, a large number of patients worldwide are suffering from unpredictable, poor bowel function postoperatively affecting their day-to-day activity and quality of life.

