### Specific Aim 1: Anorectal pathophysiology of LARS patients

Objective: use fecobionics to obtain physiological and pathophysiological signatures of anorectal function in a heterogeneous group of LARS patients. Based on the epidemiology and symptomatology of LARS, it is expected that the heterogeneous group will contain an almost equal number of LARS patients with incontinence, frequency and urgency, and those primarily with constipation and feelings of incomplete emptying. Due to the spread (heterogeneity) in the patient group regarding symptoms, regression analysis will be the primary statistical tool to associate symptoms with experimental findings. We will also compare to age- and sex-matched healthy controls from already conducted studies.

Milestone: Describe the mechanosensory signature, variation of the measured variables, and computed endpoints in LARS patients.

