**Figure 4: LARS Questionnaire**

Do you ever have occasions when you cannot control your flatus (wind)?

	No, never	0
	Yes, less than once per week	4
	Yes, at least once per week	7

Do you ever have any accidental leakage of liquid stool?

	No, never	0
	Yes, less than once per week	3
	Yes, at least once per week	3

How often do you open your bowels?

	More than 7 times per day (24 hours)	4
	4–7 times per day (24 hours)	2
	1–3 times per day (24 hours)	0
	4–7 times per day (24 hours)	5

Do you ever have to open your bowels again within one hour of the last bowel opening?

	No, never	0
	Yes, less than once per week	9
	Yes, at least once per week	11

Do you ever have such a strong urge to open your bowels that you have to rush to the toilet?

	No, never	0
	Yes, less than once per week	11
	Yes, at least once per week	16

Total Score:

Interpretation:

0–20: No LARS

21–29: Minor LARS

30–42: Major LARS

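### The only listed symptom questionnaire does not ask directly about constipation, straining or incomplete emptying, although the plan expects about half the patients to be primarily of that type

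*Combined protocol and SAP*

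**What the plan says.** Specific Aim 1 describes the intended sample by symptom type: "it is expected that the heterogeneous group will contain an almost equal number of LARS patients with incontinence, frequency and urgency", and, as the other part, "those primarily with constipation and feelings of incomplete emptying". Because of this spread, "regression analysis will be the primary statistical tool to associate symptoms with experimental findings". The section does not name the symptom variable. The study design text for Aim 1 repeats the intention to correlate device findings with symptoms, and lists expulsion time among the endpoints.

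The Data collection section lists one questionnaire: "LARS questionnaires: to assess Quality of life associated with LARS". Figure 4 prints it. The items cover flatus control, liquid leakage ("Do you ever have any accidental leakage of liquid stool"), bowel frequency ("How often do you open your bowels"), repeat opening within an hour, and urgency. A total of 0–20 is read as No LARS, 21–29 as minor and 30–42 as major.

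The inclusion criteria ask for a LARS history of more than three months and set no score threshold. The Background of research section adds that "some patients report features of both, either occurring simultaneously or fluctuating between these two groups of symptoms".

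**The concern.** The aim needs two kinds of symptom information, and the listed questionnaire asks directly about only one of them. A patient whose main trouble is evacuation can score low because the form does not ask about that trouble, not because the patient is well.

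This matters because the plan itself expects evacuation problems to affect the measurements. Its account of preliminary data (Approach, Figure 3) contrasts an incontinent subject, who loses the device without effort, with a constipated patient who fails to expel it after many attempts. The Clinical Work Flow section expects most patients without constipation to expel it within one to two minutes. If slow expellers tend to score low and fast expellers high, a regression on the total could show worse symptoms going with faster expulsion. That result would reflect item content, and nothing collected on daily evacuation symptoms would be available to check it.

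**Working it through.** **Inputs (Figure 4).** Points by answer:

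- flatus: 0 / 4 / 7
- liquid leakage: 0 / 3 / 3
- frequency: 4 (more than 7 a day), 2 (4–7 a day), 0 (1–3 a day), and a fourth option worth 5
- repeat opening within an hour: 0 / 9 / 11
- urgency: 0 / 11 / 16

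The fourth frequency option carries a label that repeats an earlier one, which may be a misprint or a fault in text extraction. From its place after 1–3 a day, I assume it means infrequent opening. The ceiling below gives the patient its full 5 points.

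**Step 1: reproduce the form's maximum.** 7 + 3 + 5 + 11 + 16 = 42, which matches the top of the major band. Without the 5-point option the sum is 7 + 3 + 4 + 11 + 16 = 41, so that option is a genuine scoring category.

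**Step 2: where the points lie.** Incontinence and urgency: 7 + 3 + 16 = 26 of 42. Frequency and repeat opening: 5 + 11 = 16 of 42. Direct questions on straining or incomplete emptying: 0.

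**Step 3: all totals open to a patient with flatus 0, leakage 0 and urgency 0.** Total = frequency + repeat opening.

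| Frequency answer | No repeat (0) | Less than weekly (9) | Weekly or more (11) |
|---|---|---|---|
| 1–3 a day (0) | 0 | 9 | 11 |
| 4–7 a day (2) | 2 | 11 | 13 |
| More than 7 a day (4) | 4 | 13 | 15 |
| Fourth option (5) | 5 | 14 | 16 |

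The largest entry is 16, so every combination falls in the 0–20 band. A patient with severe straining and incomplete emptying, 1–3 openings a day and no repeat openings scores 0, the same as a patient with no bowel symptoms.

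**Step 4: what lifts such a patient to 21.** Some incontinence or urgency is needed:

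- weekly urgency with the fourth frequency option: 16 + 5 = 21 (minor)
- weekly loss of flatus control, fourth option, repeat opening less than weekly: 7 + 5 + 9 = 21 (minor)
- flatus less than weekly, fourth option, weekly repeat opening: 4 + 5 + 11 = 20 (still No LARS)
- urgency less than weekly, fourth option, no repeat: 11 + 5 = 16 (still No LARS)

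**Step 5: set against the expected sample.** An almost equal split of 30 patients is about 15 of each type. The number of those 15 or so who would score 0–16 cannot be worked out, because the documents give no share of mixed patterns.

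**The case against.** The strongest reply is that the plan never names the LARS total as the regression variable. Item-level answers go into the database, clinical data and history are recorded, and an analysis by item is not ruled out. This stands, and it makes the ranking problem conditional. It does not supply an evacuation symptom, because no listed item asks for one directly and no rule assigns patients to a symptom type.

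Second, two items may carry some of the missing information: the 5-point frequency option and repeat opening within an hour. This stands in part. Both are indirect, and with both at their maximum the total is still 16.

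Third, other information is collected. A visual analogue scale and a symptom level are recorded during the device test. Every patient has balloon expulsion and defecography. There is a comparison pool of 20 patients with faecal incontinence and 15 with constipation. So the form is the only listed symptom questionnaire, not the only patient-reported measure. The test-time scales concern sensation during the procedure, however, and the other tests are findings, not daily symptoms.

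Two stronger readings are tempting, and the documents do not support them. A reader might infer that the regression cannot describe half the sample. The plan says primarily, not purely, constipation, and it acknowledges mixed patterns, so the affected share is unknown and may be well under half. A reader might also infer that only about 15 patients inform the regression and recompute power on that number. Nothing in the plan drops low scorers; all 30 stay in. Poor item coverage changes what the slope means, but it does not reduce the sample size.

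Finally, the study calls itself exploratory. That limits how serious the gap is, but associating symptoms with findings is still its stated main analysis.

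**Conclusion.** The point holds as a cheap improvement. As written, the trial would not directly collect the evacuation symptoms that its own aim distinguishes, and symptoms not asked at baseline cannot be reliably recovered later. The firm result is the ceiling: without incontinence or urgency a patient scores 0–16 of 42 and is classed as No LARS. It rests only on the points printed in Figure 4, and drops to 15 if the fourth frequency option is set aside.

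The effect on the regression depends on the LARS total being used as the symptom variable, and on constipation-predominant patients reporting little incontinence or urgency. Its direction (low score with slow expulsion) is plausible from the plan's own preliminary examples. Its size cannot be estimated from the documents.

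The quality-of-life description is a separate labelling error: all five items ask about bowel symptoms. Eligibility does not settle the matter either. If LARS is judged clinically, these patients enter and score as No LARS. If it is judged by the score, those with purely evacuation symptoms would not qualify, and the expected even mix is in doubt.

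**What to change.** 1. Add a short constipation/evacuation symptom score to the baseline questionnaires, or at the least items on straining and incomplete emptying.
2. State in the data analysis section that the primary regression uses two symptom variables, one for incontinence/urgency and one for evacuation, and say which LARS items enter the first. The frequency item needs an explicit decision, since it gives points for frequent opening and, on the reading above, for infrequent opening too.
3. Describe the LARS score as a bowel-symptom score. If a quality-of-life conclusion is wanted, add a short scale for it.
4. Check the label of the 5-point frequency option on the form given to patients.

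The cost is a few minutes of patient time at a visit already planned, a sentence or two of analysis text, and one more regressor. With 30 patients, an intercept and two symptom scores leave 30 − 3 = 27 residual degrees of freedom, against 28 with one score.

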### **Clinical Work Flow for the integrated device.**

This section pertains to the procedures related to use of Fecobionics. All tests prior to Fecobionics are done per department standards. The patient is instructed about the tests. The integrated device is calibrated in a one-step procedure. Similar to the conventional expulsion test, the device is placed in the rectum by manual insertion with the person lying on the side. The bag is distended with simultaneous recording of symptom level until urge to defecate. Volume is recorded. When the urge level is reached, the patient will move to the toilet chair for attempting to expel it. The patient will report sensory data. Most patients who do not suffer from constipation will be able to expel it within 1-2 minutes. If the patient fails to expel the device by himself, the physician or nurse can, if deemed necessary, pull it out by traction of a tiny thread attached to the front end (like the thread used for tampons). The thread is 50 cm long so even if the device relocates to the left side of the colon, it can still gently be pulled out. In the worst case, an endoscope can be used to pull it out.

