## **Technological background**

In the proposed studies it is important to compare the new technology, Fecobionics, to current state-of-the-art reference technologies. We expect Fecobionics to provide data that cannot be obtained with current technology and to reduce variation in measured variables.

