**Exclusion Criteria:**

1. Patients who are not willing to undergo the specified tests in this study
2. Pregnant women

The studies on LARS patients will focus on pathophysiological studies where we describe the expulsion characteristics, with focus on anal canal opening related to rectal mechanosensory data and to changes in the anorectal angle during defaecation. We will study expulsions at the urge-to-defecate level for the patients and we will correlate to data obtained by conventional technologies and to patient characteristics such as age, and symptoms as well as to risk factors. The study subjects will also be tested with conventional expulsion testing, defecography, rectal bag distension, and ARM. The studies will determine endpoints of clinical value such as expulsion time and velocity, maximum angle difference, pressure signatures and geometry changes.

**Expected Results and Milestones:** The expected outcome is that the device will perform as shown in the previous human experiments (n>60) where no adverse effects have been recorded. We anticipate successful access in LARS patients with no device-related adverse events or device malfunctions. Completion of the study is expected to derive outcome measures reflecting the defecatory function as the major impact.

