**Data analysis including statistics and sample size determination.**

A number of biomechanical parameters will be computed from the recorded data. These parameters include but are not limited to:

- Pressure difference between the rear and front ends (a measure of anal sphincter relaxation and key to the determination of phases of the defecatory process)
- Orientation and bending of Fecobionics for assessment of the anorectal angle

- Velocity of expulsion (as measured from the time difference between sensor data)
- Tension
- Strain (deformation) and displacement

Definitions of tension, strain and displacements can be found in the two books by the [name]. Sensory measures and clinical data will be related statistically to the mechanical measures. Endpoint data will be expressed as mean±SD if they can be considered normally distributed. Significance of the differences between two methods will be evaluated by ANOVA where appropriate and by multiple and single regression analysis. The results will be considered statistically significant when p<0.05 (2-tailed). Multiple regressions will be used to evaluate risk factors using causal and predictive analysis. Repeatability and distribution will be determined based on coefficient of variation (SD/mean) and used to evaluate accuracy.

The projected number of subjects, n, required to test a null hypothesis is given by the following equation:

$$n > \left[ \frac{[Z_{2\alpha} + Z_{2\beta}] \sigma}{\delta} \right]^2$$

where  $\alpha$  is the required probability of a Type I error,  $\beta$  is the required probability

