of a Type II error,  $\delta$ , is the estimated difference between the means of two comparison groups, and  $\sigma$  is the estimated standard deviation of the means in each of the two comparison groups. We assume  $2\alpha < 0.05$  ( $Z_{2\alpha} = 1.96$ ) and  $2\beta < 0.10$  ( $Z_{2\beta} = 0.84$ ). We assume the values of mean difference, d, and standard deviation, s, from previous experience in the clinical laboratory and from reported data in the literature on the involved patient groups and the sensitivity and specificity of current tests. An alternative method is to use sample size estimation based on the Altman-Bland analysis (<http://wwwusers.york.ac.uk/~mb55/meas/sizemeth.htm>). Preliminary data on expulsion time using BET and Fecobionics were used in the sample size analysis. Data variation (SD, SE) was computed for preliminary data. The confidence interval for the 95% limits of agreement was computed and n was determined. For both analyses, given the exploratory nature of the study, we consider a heterogeneous group of patients and that 80% of operated patients will develop LARS. Using these boundaries and criteria, we arrived at a sample size of 30 in the Aim 1 study for evaluation of statistical significance, association and risks. Though the material may be too small to account for confounders, we will obtain clear indications of risks and causes. For the comparison with previously studied subjects, we have a pool of 35 healthy asymptomatic subjects, 20 patients with FI and 15 patients with constipation to compare with.

**Clinical Assessments of device safety:** Fecobionics have now been used in more than 70 human studies without any incidents or adverse effects. In addition, a safety study has been performed in 12 pigs without any device related issues or damage to anorectal mucosa (yet unpublished data). Since Fecobionics is still an experimental device, we will pay attention to safety. If any safety issue occurs, it will be characterized and reported. Additional data obtained will include procedural duration, sensation

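### The order of the balloon expulsion test and Fecobionics is neither stated, balanced nor recorded, so an order effect could pass for a method difference in expulsion time

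*Combined protocol and SAP*

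**What the plan says.** The comparison is within patients. Under Data collection, "All patients will undergo the following tests" introduces a list of Fecobionics, manometry, BET and defecography. The text after the exclusion criteria repeats this: "The study subjects will also be tested with conventional expulsion testing, defecography, rectal bag distension, and ARM".

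Comparing methods is a declared purpose. Technological background states that "it is important to compare the new technology, Fecobionics, to current state-of-the-art reference technologies". The data analysis section adds: "Significance of the differences between two methods will be evaluated by ANOVA where appropriate and by multiple and single regression analysis". On sample size it says: "Preliminary data on expulsion time using BET and Fecobionics were used in the sample size analysis", and it mentions an agreement approach based on 95% limits of agreement.

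On sequence there is one sentence, in the Clinical Work Flow section: "All tests prior to Fecobionics are done per department standards". It does not name those tests or say that the order is the same for everyone. The Data collection list puts Fecobionics first, but as a list and not a schedule. Nowhere does the plan give a fixed or balanced order, an interval, a same-day or separate-day rule, an instruction to record the order, or an order or period term in the analysis.

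**The concern.** BET and Fecobionics make similar demands on the patient: a device is placed in the rectum and the patient tries to expel it. The result depends on effort and sensation, so the second attempt may differ from the first through practice, fatigue or irritation. If one test always comes second, its measured difference from the other contains that change. A larger sample estimates the wrong quantity more precisely. An unrecorded, haphazard order is also a problem, because it cannot be adjusted for afterwards.

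At stake is the BET-versus-Fecobionics comparison of expulsion time, which is also the pairing behind the sample size. The symptom regressions that Specific Aim 1 calls primary are much less exposed.

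**Working it through.** **The plan's own figure.** The sample size of 30 cannot be reproduced, because the plan gives no values for the difference δ or the SD σ. Solving its formula backwards with its Z values of 1.96 and 0.84:

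δ/σ = (1.96 + 0.84)/√30 = 2.80/5.477 = 0.51.

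So 30 patients correspond to a difference of about half an SD. Order effects of a few tenths of an SD are not negligible on that scale.

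**Inputs.** From the plan: n = 30 and two-sided p<0.05. Assumed: the true method difference is zero, paired differences are roughly normal, and the order effect π (second test minus first) is between 0 and 0.5 SD of the paired difference. The documents give no size or direction for π.

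**What each order estimates.** Let d = Fecobionics minus BET, and τ the true method difference.

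- BET always first: mean of d = τ + π. Only the sum can be estimated.
- Half in each order: mean of d is τ + π when BET is first and τ − π when Fecobionics is first. Half the sum of the two means is τ, and half their difference is π.
- If the effect of going second differs by order (π₁ with BET first, π₂ with Fecobionics first), half the sum is τ + (π₁ − π₂)/2. Cancellation is therefore exact only for equal carryover.

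**False-positive rate, BET always first.** Two-sided paired t test on 29 degrees of freedom, noncentrality π√30:

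| π (SD) | π√30 | P(p<0.05), τ = 0 |
|---|---|---|
| 0 | 0 | 0.0500 |
| 0.1 | 0.548 | 0.0827 |
| 0.2 | 1.095 | 0.1852 |
| 0.3 | 1.643 | 0.3555 |
| 0.4 | 2.191 | 0.5628 |
| 0.5 | 2.739 | 0.7540 |

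**Check by simulation (40,000 runs).** With BET always first, the rates at π = 0.2, 0.3 and 0.5 were 0.189, 0.360 and 0.754. With 15 patients in each order, equal carryover and a period-adjusted analysis, bias was about 0 and the rates were 0.049, 0.049 and 0.051.

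**Precision.** The standard error in the balanced design is s × √(2/15)/2 = 0.183s, the same as s/√30 = 0.183s with a single order. The only loss is one degree of freedom, 28 instead of 29.

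**Limits of agreement.** Both limits are the mean difference ± 1.96s, so a common π moves both by π. For comparison, the 95% confidence interval for each limit at n = 30 is about ±1.96 × √(3/30) × s = ±0.62s. That interval does not allow for the shift.

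**The case against.** A reader might infer that the plan fixes the order with BET first, so that order and device are completely confounded. The documents do not go that far. The sentence on prior tests does not name BET, does not say the order is common to all patients, and stands in a section confined to Fecobionics procedures. Tests on separate days would weaken fatigue and irritation, and the plan does not say whether they share a day. The confounding is therefore conditional. What stands is that nothing in the plan rules it out or records the information needed to adjust.

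A reader might also infer that the main results are biased. Specific Aim 1 makes regression of symptoms on findings the primary tool, and a shift equal in all patients does not bias those slopes or the correlations with conventional tests. Only a shift that varies with symptoms would.

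A third tempting inference is that swapping the two expulsion tests also protects urge volume and sensation. It does not: the plan lists urge volume with the manometry and BET parameters and assigns sensitivity and rectal capacity to manometry, so the order of manometry and Fecobionics stays unbalanced.

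Three further objections narrow the benefit without removing it. Manometry and BET are described together under Reference testing techniques, so a swap may mean separating them. Equal carryover is an assumption, and 15 patients per order give little power to test it. BET uses a fixed 50 ml while Fecobionics is filled to urge, so that volume difference remains part of the method difference in either order. Finally, the percentages are paired t test power at assumed effects, not evidence that an order effect exists.

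**Conclusion.** The point holds for expulsion time. The plan makes a within-patient method comparison and leaves the order of the two expulsion tests unstated, unbalanced and unrecorded. If BET always precedes Fecobionics, the bias in the mean difference and in both limits of agreement equals the order effect, whatever the sample size. The chance of a false difference then rises from 5% to about 19% to 75% over assumed effects of 0.2 to 0.5 SD. These figures rest on a single common order, a true difference of zero, roughly normal paired differences and order effects chosen for illustration.

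This is an inexpensive improvement to a declared comparison in a study that calls itself exploratory. It is not a flaw in the primary symptom regressions.

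**What to change.** - Allocate the order of BET and Fecobionics by a prepared list, 15 patients each way.
- Keep manometry and defecography at the same point in the sequence for all patients, and state that sequence.
- Record the actual order and the interval between tests for every patient.
- Include a period term in the paired expulsion-time analysis, and an order covariate in regressions that use Fecobionics measures. The covariate matters because balancing otherwise adds order-related variation to those measures.
- Report as limitations that urge volume and sensation against manometry are not balanced, and that the volume difference remains part of the BET-versus-Fecobionics difference.

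**Cost.** No extra patients or tests. BET may have to be separated from manometry, the device must sometimes be ready first, and one degree of freedom is spent. Comparison with the previously studied subjects (35 healthy, 20 with incontinence, 15 with constipation) should account for order, since half of the new patients would have Fecobionics before BET. Cancellation still assumes similar carryover in both directions.

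If balancing proves impracticable, state and record the order and the interval, and report the order as a limitation of the method comparison.
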